APPENDIX 2. POST-INJECTION PHONE CALL SCRIPT

Within 24-72 hours after each injection visit, the **masked** Investigator (or designee) should call the subject to ask about post-injection complaints. During the telephone contact, the Investigator (or designee) will determine whether there is a need to bring the subject in for an unscheduled study visit. If the subject cannot be reached on the first attempt, the Investigator (or designee) must make at least 2 additional attempts to reach the subject. Each attempt should be documented in the eCRF with the date and time of the contact noted.

A successful telephone contact is one in which the Investigator (or designee) has spoken directly to the subject and has determined the need for an unscheduled post-injection visit based on the answers to the questions outlined below. A telephone contact with someone other than the subject does not qualify as a successful telephone contact.

The following questions should be asked in the order noted.

Adverse Events

1. How are you feeling in general?
2. Do you have any complaints since the injection?

The Investigator (or designee) should not in any way prompt or probe the subject about anything, in particular not about changes in vision. Any complaints (e.g. blurred vision) should be recorded in the eCRF as for any AE, with time of onset, severity etc. If the subject has taken a concomitant medication for treatment of a complaint (e.g. aspirin for a headache), then the medication should be recorded on the eCRF page with the appropriate indication.

Concomitant Medications

1. Did you take any NEW medications since the injection?
2. Did you change any medications you were taking since the injection (did you take more or less of the medications? Or stop any medications?)

The masked Investigator (or designee) should verify that there are no changes to the concomitant medications since the last study visit. If there has been a change in any medication or an additional medication that was taken, the masked Investigator (or designee) should complete all the information as required on the eCRF page for concomitant medications. If there is a new medication that has been taken the indication should also be noted on the eCRF page.

Once the Investigator (or designee) has asked about complaints and concomitant medications, a decision should be made as to whether or not the subject should return for an unscheduled post-injection visit.

TG ThromboGenics®	Cover Page
TG-MV-015_Abbreviated SAP_17-JAN-2019	

DOCUMENT TYPE

ABBREVIATED STATISTICAL
ANALYSIS PLAN (SAP)

PROTOCOL TITLE:

A PHASE 2, RANDOMISED,
DOUBLE-MASKED,
SHAM-CONTROLLED, MULTI-CENTRE
STUDY TO EVALUATE THE EFFICACY
AND SAFETY OF OCRIPLASMIN IN
INDUCING TOTAL POSTERIOR
VITREOUS DETACHMENT (PVD) IN
SUBJECTS WITH NON-PROLIFERATIVE
DIABETIC RETINOPATHY (NPDR)
(CIRCLE)

PROTOCOL NUMBER:

TG-MV-015

CLINICALTRIALS.GOV
IDENTIFIER:

NCT02681809

SAP DATE:

17-JAN-2019

ABBREVIATED STATISTICAL ANALYSIS PLAN FOR FINAL ANALYSIS

PROTOCOL TITLE: A PHASE 2, RANDOMISED, DOUBLE-MASKED, SHAM-CONTROLLED, MULTI-CENTRE STUDY TO EVALUATE THE EFFICACY AND SAFETY OF OCRIPLASMIN IN INDUCING TOTAL POSTERIOR VITREOUS DETACHMENT (PVD) IN SUBJECTS WITH NON-PROLIFERATIVE DIABETIC RETINOPATHY (NPDR) **(CIRCLE)**

PROTOCOL NUMBER: TG-MV-015

STUDY PHASE: PHASE 2

EudraCT NUMBER: 2015-002415-15

IND NUMBER: 126449

SPONSOR: THROMBOGENICS NV, [name]
[name]

FINAL PROTOCOL DATE: 04-SEP-2015

AMENDMENT 1 DATE: 13-OCT-2015

AMENDMENT 2 DATE: 28-OCT-2016

Abbreviated SAP 17Jan2019

CONFIDENTIAL

The information contained in this document is CONFIDENTIAL and is the property of ThromboGenics. Except to the extent necessary to obtain informed consent, information may not be disclosed unless such disclosure is required by government regulation or state/local customs or law. No part of it may be transmitted, reproduced, published, or used by anyone without the written permission of ThromboGenics. Persons to whom the information is disclosed must be informed that the information is CONFIDENTIAL and may not be further disclosed by them.

Table of Contents

1. Background	3
2. Objective	3
3. Conventions for Analysis and Computations	3
4. Appendix	7
4.1. Conventions for Imputing Partially Missing and Missing Dates	7

1. Background

This document describes the tables and listings generated for the Final Analysis. The final analysis took place after all subjects completed the Month 24 visit (Visit 11). This document is an abbreviated version of the original SAP, which also contained mock-up tables and listings. In addition, information which is considered of intellectual property nature is not included in this abbreviated version of the SAP.

2. Objective

The objective of this document is to define the set of summary tables and individual data listings that will support the writing of the clinical study report.

3. Conventions for Analysis and Computations

All Treated Subjects Analysis Set

A single analysis set will be used. The All Treated Subjects analysis set will include subjects who are randomized and receive the first injection of study treatment. Subjects will be assigned to the treatment they receive at the time of the first injection.

Baseline Value

Baseline value is defined as the last non-missing value prior to administration of the first injection of the study drug.

Change from Baseline

Change from Baseline is calculated as the difference between the value at a considered visit minus the Baseline value. Change from Baseline will be missing if either one of the Baseline Value or the value at the considered visit is missing.

Adverse Events

Adverse events are coded using MedDRA version 18.1.

If a subject has multiple occurrences of an AE after an injection, the subject is presented only once in the respective subject count. Events are counted each time in the event column. Ocular adverse events are those that occur in either eye. Events recorded as OU (both eyes) are counted once for the study eye and once for the non-study eye, and are counted as 2 separate ocular events.

Drug related events are events considered by the Investigator with a reasonable possibility that the study treatment caused the event or events with a missing relationship.

Where severity is missing, the adverse event will be assigned to the ‘severe’ category.

AEs will be attributed to the closest injection prior to the occurrence of the event. AEs with a start date corresponding to the date of one of the injections will be attributed to that particular injection.

Treatment Emergent Adverse Events

Treatment Emergent Adverse Events are adverse events with a start date on or post the date of the first injection, or a missing start date.

Concomittant Interventions/Anti-VEGFs

Concomittant Interventions (including Anti-VEGFs) are interventions with a start date on or post the date of the first injection, or a missing start date.

Imputation of Partially Missing Dates

The conventions for imputing partially missing dates are provided in the appendix of this document.

Age Computation

The Date of Birth (DOB) will be imputed to 01JULYYYY where YYYY correspond to the year of birth. The following SAS code will be used for calculating age.

$$\text{floor}(\text{intck}(\text{'month'}, \text{DOB}, \text{first injection date}) - (\text{day}(\text{first injection date}) < \text{day}(\text{DOB}))) / 12$$

By Visit Layout

In tables summarizing data ‘By Visit’, post-injection 2 and 3 visits will be presented on 2 rows. The first row will be labelled ‘Day/Month xx, Post-Injection 2/3’ and will present data of subjects with 2 or 3 injections, respectively. The second row will be labelled ‘Day/Month xx, Missing Repeat Injection(s)’ and will present data of subjects who did not receive the complete set of repeat injections.

Early Termination Visit

The Early Termination visit corresponds to the last visit attended by subjects who discontinue from the study. Early Termination visits will be re-coded when possible. The related data will be summarized in the corresponding re-coded visit and in a visit named ‘*Early Termination*’. For example, if a subject discontinues with its last visit being the Day 28 visit, then the corresponding data will appear in the line ‘*Day 28, Post-Injection 1*’ and in the line ‘*Early Termination*’ of the summary tables.

Unscheduled Visit

Unscheduled visits will not appear in the summary tables, but in the listings.

Summary Statistics

Descriptive statistics for continuous variables and calculated change from baseline variables will include:

- number of subjects with available data
- mean and standard deviation
- median
- minimum and maximum

- 95% CI for mean, where indicated.

Categorical data and shift from baseline will be summarized by presenting:

- count
- percentage (where the denominator is based on the total number of subjects in the treatment group or overall, unless otherwise stated in the table footnotes)
- 95% CI for the proportion (Clopper-Pearson method), where indicated.

Protocol Deviations

Deviations from the protocol will be documented on an ongoing basis by the study monitors and project managers throughout the study. Protocol deviations are recorded outside the clinical database and will be reviewed by ThromboGenics during the course of the study, prior to database lock.

Missing Data

Missing data will not be replaced (unless otherwise specified), and data analysis will be performed based on the observed cases (OC) principle.

Subgroup Analysis

No subgroup analyses, nor analysis per center, will be performed.

Sensitivity Analysis

No sensitivity analyses will be performed.

Changes in Planned Analyses from the Protocol

The early stopping of the subject enrolment has led to the following changes to the analyses planned in the protocol.

A single analysis dataset will be used instead of the 3 listed in the protocol.

The first and third quartiles, and 5th and 95th percentiles will not be included in the summary statistics of continuous variables.

No statistical testing will be performed.

The last-observation-carried-forward method for data imputation will not be used, and no sensitivity analysis will be performed.

The stratification variable, NPDR severity, will not be taken into account in any summary statistics.

The following exploratory endpoints will not be summarized:

- $A \geq 2$ -step progression on the ETDRS Severity Scale from baseline, at Month 15 and at Month 24, based on 7-standard field stereo colour fundus photography, as assessed by the masked CRC

- Improvement of ≥ 2 steps on the ETDRS Severity Scale from baseline, at Month 15 and at Month 24, based on 7-standard field stereo colour fundus photography, as assessed by the masked CRC
- Neovascularisation as compared to baseline, at Month 15 and at Month 24, based on 7 standard field stereo colour fundus photography, as assessed by the masked CRC
- Vitreous / pre-retinal haemorrhage by Month 24, based on 7-standard field stereo colour fundus photography, as assessed by the masked CRC
- Development of iris neovascularisation as compared to baseline, at each study visit, based on slit lamp examination

4. Appendix

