3.5. Treatment Allocation

3.5.1. Treatment Allocation at First Injection

The target is to enrol approximately 115 eligible subjects who will be sequentially assigned, according to a computer-generated randomisation list, to the ocriplasmin 0.0625mg arm, the ocriplasmin 0.125mg arm or the sham arm in a 2:2:1 allocation ratio (approximately 46 subjects in each ocriplasmin arm and approximately 23 subjects in the sham arm).

Randomisation will be stratified by baseline NPDR severity (moderate and moderately severe NPDR, *i.e.* ETDRS Level 43A-47D *vs.* severe and very severe NPDR, *i.e.* ETDRS Level 53A-E). It is expected that more subjects with moderate and moderately severe than with severe and very severe NPDR will be enrolled, as a reflection of the natural population. Therefore, enrolment in the moderate and moderately severe NPDR stratum may become capped in the course of the study.

Allocation of eligible subjects to a treatment arm will be performed through an interactive voice / web response system (IXRS). The unmasked treating investigator / designee will access the system to obtain the subject's treatment allocation and the treatment number for the first injection. The assigned treatment number will be loaded automatically by IXRS into the subject's electronic case report form (eCRF).

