For screening failures due to reasons that are expected to be temporary, and for subjects for whom eligibility cannot be timely determined due to a problem with one of the eligibility assessments (*e.g.* ungradable B-scan ultrasound), 1 re-screening visit can be organised. The re-screening visit should be scheduled at least 28 days after the 1st screening visit. Subjects who are re-screened will be given a new subject number and need to have all screening procedures repeated (including signing of a new Informed Consent Form).

For eligible subjects, all information must be recorded in the subject's eCRF. For subjects who do not meet the eligibility criteria, the minimum information to be recorded in the eCRF will be the following: date of screening, subject number, procedures completed and reason for screening failure.

5.3. Visit 2 –Day 0

The following procedures will be performed:

- Urine pregnancy test (for women of childbearing potential only)
Pregnant women will not be eligible for study participation
- Blood sampling for immunogenicity assessment
Refer to the study-specific manuals for instructions on the collection, processing, storage and shipping of blood samples
- BCVA (ETDRS) –**both eyes**
- Colour vision (Roth 28-hue) – **study eye only** (only at sites where the Roth 28 Colour Test is available)
Not needed for subjects > 80 years of age or with a diagnosis of dyschromatopsia at baseline
- Full ophthalmic examination – **study eye only**

- SD-OCT (widefield) – **study eye only** (only at sites where this is available)
- ffERG – **both eyes** (in approximately 25% of the subjects, at sites where this is available)
- Treatment number allocation (refer to [Section 3.5.1](#))
Randomisation can only occur after confirmation of eligibility by the B-scan expert reader and the CRC
- Study treatment
- Post-injection assessment (IOP measurement and indirect ophthalmic examination)
The post-injection assessment should be performed by the unmasked treating investigator as many times as needed at his / her discretion but at least once within 60 minutes after the injection to exclude central retinal artery non-perfusion or other complications
- Record concomitant medications / treatments / interventions (refer to [Section 6.4](#))
- (S)AE monitoring (refer to [Section 8.4](#))

All information must be recorded in the subject's eCRF.

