6.2.3. Study Drug Preparation and Administration

The unmasked treating investigator / designee will prepare the injections. The unmasked treating investigator will administer the injections (ocriplasmin 0.0625mg, ocriplasmin 0.125mg and sham).

In addition to the procedures described below, added safety measures in adherence to specific institutional policies associated with intravitreal injections will be used. Also refer to ([Avery *et al.*, 2014](#)) for a guideline on intravitreal injection technique and monitoring.

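### Neither the SAP nor the protocol has an all-randomised analysis set, and the person giving the first injection can know the arm, so a small arm-dependent exclusion from the efficacy summaries cannot be ruled out

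*SAP*

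**What the plan says.** **Analysis set.** SAP section 3 states "A single analysis set will be used" and defines it: "The All Treated Subjects analysis set will include subjects who are randomized and receive the first injection of study treatment". On grouping it adds: "Subjects will be assigned to the treatment they receive at the time of the first injection". The same section excludes sensitivity analyses and statistical testing, works on observed cases, and says under the changes from the protocol: "A single analysis dataset will be used instead of the 3 listed in the protocol".

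**Protocol sets.** The Safety Analysis Set (9.2.1) and the Full Analysis Set (9.2.2) each require at least one dose. The Full Analysis Set also requires a post-baseline efficacy assessment and analyses subjects as randomised. The Per Protocol Set (9.2.3) is a subset of the Full Analysis Set.

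**Day 0.** Protocol 3.5.1 says: "The unmasked treating investigator / designee will access the system to obtain the subject's treatment allocation and the treatment number for the first injection". Section 6.2.3 gives the injection itself to the unmasked treating investigator, and Table 8 lists system access and injection procedures as unmasked tasks. Section 5.3 (Visit 2) places treatment number allocation and study treatment in the same visit, with the condition "Randomisation can only occur after confirmation of eligibility by the B-scan expert reader and the CRC". Table 6 adds the central laboratory to that condition.

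**The concern.** Leaving never-treated subjects out of an efficacy set is usually defended on the ground that masking makes the start of treatment independent of the arm. That defence is not available for the person giving the injection in this trial.

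The arms also differ at that moment. Sham does not penetrate the globe (3.6.1), and the protocol chose it because of the risks of a real intravitreal injection (1.4.3). A late doubt about an eye could therefore weigh differently once the arm is known. If subjects were left uninjected for that reason, they would tend to come from the ocriplasmin arms. Dropping subjects without total PVD raises the rate of the arm that they leave.

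With one set and no sensitivity analysis, the published plan shows no efficacy summary in which such subjects would reappear.

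**Working it through.** **Who can be left out.**

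| Set | Dose required | Other condition | Grouping |
|---|---|---|---|
| Protocol Safety (9.2.1) | yes | none | as treated at Day 0 |
| Protocol Full Analysis (9.2.2) | yes | at least one post-baseline efficacy assessment | as randomised |
| Protocol Per Protocol (9.2.3) | yes, as a subset of the Full Analysis Set | no major deviations | as randomised |
| SAP All Treated Subjects | yes | none | as treated at first injection |

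No set in either document contains all randomised subjects. On who is included, the SAP set is wider than the protocol's primary efficacy set. On grouping, the SAP has given up analysis as randomised.

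**Arm sizes.** The 2:2:1 ratio reproduces the planned numbers: 115 × 2/5 = 46 per ocriplasmin arm and 115 × 1/5 = 23 for sham. The protocol's clarification note gives 48 randomised but no split by arm. Applying the ratio gives 48 × 2/5 = 19.2 and 48 × 1/5 = 9.6, so I assume 19/19/10.

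**Assumed responders.** Protocol 9.1 assumes total PVD in 40% on ocriplasmin and 5% on sham: 0.40 × 19 = 7.6 and 0.05 × 10 = 0.5. I therefore use 7 or 8 responders on ocriplasmin and 0 or 1 on sham. These are illustrations, not trial data.

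**Shift.** Let *n* be randomised to an arm, *x* have total PVD, and *k* be never injected and without total PVD. The SAP rate is *x*/(*n* − *k*) and the all-randomised rate is *x*/*n*. The shift is *x*/(*n* − *k*) − *x*/*n* = *xk*/[*n*(*n* − *k*)].

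| Arm | *x*/*n* | *k* = 1 | *k* = 2 | *k* = 3 |
|---|---|---|---|---|
| Ocriplasmin | 7/19 = 36.8% | 7/18 = 38.9% | 7/17 = 41.2% | 7/16 = 43.8% |
| Ocriplasmin | 8/19 = 42.1% | 8/18 = 44.4% | 8/17 = 47.1% | 8/16 = 50.0% |
| Sham | 1/10 = 10.0% | 1/9 = 11.1% | 1/8 = 12.5% | 1/7 = 14.3% |
| Sham | 0/10 = 0% | 0% | 0% | 0% |

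For one omitted subject, the shift is 7/(19 × 18) = 2.0 points or 8/(19 × 18) = 2.3 points on ocriplasmin, and 1/(10 × 9) = 1.1 points or zero on sham. With *k* = 0 there is no shift.

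**Effect on the difference** (7/19 against 1/10). All randomised: 36.8 − 10.0 = 26.8 points. One ocriplasmin subject omitted: 38.9 − 10.0 = 28.9. One sham subject omitted: 36.8 − 11.1 = 25.7. So the sign depends on the arm that loses the subject.

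**Scale.** The Clopper-Pearson 95% interval, the SAP's method, is 16.3% to 61.6% for 7/19 and 0.3% to 44.5% for 1/10. A move of 1 to 2 points is small beside either.

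**The case against.** A reader might infer that the unmasked treating investigator decides whether to inject, knowing the arm, and so filters who enters the analysis. The documents do not support that. They assign system access and administration, but no Day 0 choice to inject or withhold, and a masked subject could also decline. The withdrawal list in 4.2.1 concerns repeat injections, and masked staff assess it (Table 8).

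Several safeguards narrow the window. Eligibility is confirmed before randomisation. Section 5.3 lists the Day 0 pregnancy test, visual acuity and ophthalmic examination ahead of allocation. Waivers are barred except for immediate hazards (3.9), and an unmasked monitor checks that assigned treatments were given (6.2.5). Selective withholding would have to happen between two steps of one visit.

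A reader might also infer that moving from three sets to one discarded a wider efficacy set. It did not, because none of the three included uninjected subjects.

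Nor is it established that these subjects go unreported. Protocol 9.4 plans disposition by arm, and the public SAP is abbreviated, without its mock-up tables and listings. A count of randomised against treated may already exist.

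Finally, scoring never-injected subjects as failures departs from the observed-case rule, and no test result is affected because none is run.

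All of this stands, and it limits the point. It does not supply an all-randomised summary or restore masking at the injection step.

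**Conclusion.** The point holds as a low-cost improvement. The only analysis set omits subjects randomised but not injected, a restriction carried over from the protocol, and masking does not protect the start of treatment from knowledge of the arm. Arm-dependent exclusion is possible, but nothing in the documents shows that it occurred. The number affected is not stated and may be zero.

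The size is about 1 to 2 percentage points in an arm's rate for one omitted subject. This rests on the assumed 19/19/10 split, the assumed responder counts, and the omitted subject not having total PVD. The by-arm proportions are descriptive, so what is affected is their denominators and how they are read.

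**What to change.** Summarise total PVD by Month 3 for all randomised subjects, grouped as randomised. Count a never-injected subject as not having total PVD unless study imaging shows it, and state this as an exception to the SAP's observed-case rule. Keep All Treated Subjects for safety. Report by arm the number randomised but not injected, with reasons. If that number is zero, saying so settles the exclusion question.

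The SAP's background section says that the final analysis has taken place, so a supplementary table and a disposition line in the study report would do. The cost is that one table, a sentence on the imputation, and possibly slightly lower rates. Follow-up imaging may be missing for never-injected subjects, because the protocol spells out continued follow-up for those withdrawn from repeat injection (4.2.1) but not for those never injected. The counting rule would then decide their outcome and should be stated openly.

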6.2.3.2. Ocriplasmin 0.0625mg Injection

Study drug preparation will be done outside of the subject's view. In addition, a sterile drape may be used to cover the fellow eye and the subject will be instructed to direct his / her gaze away at all times. It is recommended to follow the guidelines published by Avery *et al* on intravitreal injections (Avery *et al.*, 2014). The injection should be carried out under aseptic conditions, which includes the use of surgical hand disinfection, sterile gloves, a surgical mask, a sterile drape and a sterile eyelid speculum (or equivalent).

1. Remove the drug kit from the freezer and allow to thaw at room temperature (takes about 2 minutes)
2. Once completely thawed, remove the protective polypropylene flip-off cap from the ocriplasmin vial and discard the flip-off cap immediately
3. Disinfect the top of the ocriplasmin vial with an alcohol wipe
4. Disinfect the top of the NaCl (0.9%) ampoule with an alcohol wipe. Twist off the head of the ampoule to decapsulate. Insert the syringe cone into the ampoule and withdraw NaCl (0.9%). Detach the syringe from the ampoule and attach 1 of the 19G needles. Carefully expel the air and excess NaCl (0.9%) from the syringe and adjust the volume to the 0.6mL mark
5. Add 0.6mL NaCl (0.9%) into the ocriplasmin vial. Discard the needle and the syringe
6. Swirl the vial
7. Visually inspect the vial for particulate matter. Only a clear, colourless solution without visible particles should be used
8. Using aseptic technique, withdraw all of the solution using the other 19G needle (slightly incline the vial to ease withdrawal) and discard the needle after withdrawal of the vial contents. Do not use this needle for the intravitreal injection
9. Replace the needle with the sterile 30G injection needle, carefully expel the air and excess drug from the syringe and adjust the volume to the 0.1mL mark on the syringe (corresponding to 0.0625mg ocriplasmin)
10. Inject 0.1mL of the solution into the mid-vitreous:
 - a. The injection should be made through the pars plana in the inferotemporal quadrant 3.5-4mm posterior to the limbus
 - b. The needle should be inserted at least 6mm towards the centre of the eye avoiding the horizontal meridian

- c. Use a moderately slow injection technique in order to allow the test product to enter the vitreous
11. Slowly remove the needle and use a sterile cotton-tip applicator to prevent reflux of both the test product and the vitreous

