6.2.3.3. Ocriplasmin 0.125mg Injection

Study drug preparation will be done outside of the subject's view. In addition, a sterile drape may be used to cover the fellow eye and the subject will be instructed to direct his / her gaze away at all times. It is recommended to follow the guidelines published by Avery *et al* on intravitreal injections (Avery *et al.*, 2014). The injection should be carried out under aseptic conditions, which includes the use of surgical hand disinfection, sterile gloves, a surgical mask, a sterile drape and a sterile eyelid speculum (or equivalent).

1. Remove the drug kit from the freezer and allow to thaw at room temperature (takes about 2 minutes)
2. Once completely thawed, remove the protective polypropylene flip-off cap from the ocriplasmin vial and discard the flip-off cap immediately
3. Disinfect the top of the ocriplasmin vial with an alcohol wipe
4. Disinfect the top of the NaCl (0.9%) ampoule with an alcohol wipe. Twist off the head of the ampoule to decapsulate. Insert the syringe cone into the ampoule and withdraw NaCl (0.9%). Detach the syringe from the ampoule and attach 1 of the 19G needles. Carefully expel the air and excess NaCl (0.9%) from the syringe and adjust the volume to the 0.2mL mark
5. Add 0.2mL NaCl (0.9%) into the ocriplasmin vial. Discard the needle and the syringe
6. Swirl the vial
7. Visually inspect the vial for particulate matter. Only a clear, colourless solution without visible particles should be used
8. Using aseptic technique, withdraw all of the solution using 1 of the 19G needles (slightly incline the vial to ease withdrawal) and discard the needle after withdrawal of the vial contents. Do not use this needle for the intravitreal injection
9. Replace the needle with the sterile 30G injection needle, carefully expel the air and excess drug from the syringe and adjust the volume to the 0.1mL mark on the syringe (corresponding to 0.125mg ocriplasmin)
10. Inject 0.1mL of the solution into the mid-vitreous:
 - a. The injection should be made through the pars plana in the inferotemporal quadrant 3.5-4mm posterior to the limbus

- b. The needle should be inserted at least 6mm towards the centre of the eye avoiding the horizontal meridian
 - c. Use a moderately slow injection technique in order to allow the test product to enter the vitreous
11. Slowly remove the needle and use a sterile cotton-tip applicator to prevent reflux of both the test product and the vitreous

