9.2. Subject Analysis Sets

9.2.1. Safety Analysis Set

The Safety Analysis Set consists of all subjects who received at least 1 dose of study drug. Analyses on the Safety Analysis Set will be performed based on treatment actually administered at Visit 2 (Day 0).

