9.2.2. Full Analysis Set

The Full Analysis Set consists of all subjects who received at least 1 dose of study drug and for whom data of at least 1 post-baseline efficacy assessment is present. Analysis on the Full Analysis Set will be based on the assigned randomised treatment.

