9.5. Analysis of Efficacy

Efficacy analyses will be performed on the Full Analysis Set.

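### The SAP groups efficacy by the first injection received, where the protocol groups it as randomised, and the lists of changes do not mention the switch

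*SAP*

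**What the plan says.** **Protocol.** Section 9.5 states: "Efficacy analyses will be performed on the Full Analysis Set". Section 9.2.2 fixes the arm for that set: "Analysis on the Full Analysis Set will be based on the assigned randomised treatment". Section 9.2.3 applies the same rule to the Per Protocol Set. Only the Safety Analysis Set (9.2.1) is grouped by what was actually given at Day 0.

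**SAP.** Section 3, under All Treated Subjects Analysis Set, says: "A single analysis set will be used". It contains subjects who were randomised and had the first injection, and the arm rule is: "Subjects will be assigned to the treatment they receive at the time of the first injection". No separate rule is given for efficacy tables, and section 3 also rules out sensitivity analyses.

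**Disclosure.** Under Changes in Planned Analyses from the Protocol, the SAP says: "A single analysis dataset will be used instead of the 3 listed in the protocol". The clarification note at the front of the protocol says the same. Neither mentions randomised versus received treatment. The reason given for the changes as a whole is the early stop of enrolment.

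**The concern.** Collapsing three sets into one did more than simplify the populations. The protocol's grouping rule for safety now also governs total PVD, progression to PDR, BCVA change and the other efficacy endpoints that are still summarised. Under that rule, arm membership can depend on something that happens after randomisation, namely an allocation or preparation error at Day 0.

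Early stopping may justify fewer analysis sets. It does not explain a change in how arms are defined. Both lists of changes itemise matters as small as dropping quartiles, so a reader of those lists alone could reasonably assume that efficacy is still shown as randomised.

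A discrepancy between the two doses is conceivable because both are prepared on site from the same type of vial. Section 6.2.3.2 says "Add 0.6mL NaCl (0.9%) into the ocriplasmin vial" and section 6.2.3.3 says "Add 0.2mL NaCl (0.9%) into the ocriplasmin vial". Protocol 1.4.2.1 says that comparing the two doses will help choose the dose for Phase 3. With no testing, the by-arm proportions are the efficacy evidence for that purpose.

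**Working it through.** **Step 1: the rules side by side**

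| | Protocol | SAP section 3 |
|---|---|---|
| Efficacy: who | Treated, with at least one post-baseline efficacy assessment (9.2.2) | Randomised and given the first injection |
| Efficacy: arm | As randomised (9.2.2, 9.5) | First injection received |
| Safety: who | Treated (9.2.1) | Same single set |
| Safety: arm | As administered at Day 0 (9.2.1) | First injection received |
| As-randomised efficacy result available elsewhere | Not needed | No sensitivity analysis planned |

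The safety row is essentially unchanged. The efficacy arm rule is reversed. Randomised but untreated subjects are left out under both documents, so the point concerns arm assignment and not that exclusion.

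**Step 2: arm sizes.** The plan's own split follows from the 2:2:1 ratio (protocol 3.5.1): 115 × 2/5 = 46 and 115 × 1/5 = 23, as stated. The clarification note gives 48 randomised. The same ratio gives 48 × 2/5 = 19.2 and 48 × 1/5 = 9.6, or about 19/19/10. The actual arm counts are not in the documents, so this split is an assumption.

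**Step 3: one subject re-classified between the two dose arms.** Take the protocol's assumed 40% total PVD rate (9.1): 0.40 × 19 = 7.6, so use 8 responders per dose arm as randomised, 8/19 = 42.1% in each. Suppose one subject randomised to dose A is recorded as having received dose B first.

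| Subject who moves | Dose A | Dose B | B minus A |
|---|---|---|---|
| None | 8/19 = 42.1% | 8/19 = 42.1% | 0.0 |
| One responder | 7/18 = 38.9% | 9/20 = 45.0% | +6.1 |
| One non-responder | 8/18 = 44.4% | 8/20 = 40.0% | −4.4 |

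Change within each arm, in percentage points:
- responder: 38.9 − 42.1 = −3.2 and 45.0 − 42.1 = +2.9
- non-responder: 44.4 − 42.1 = +2.3 and 40.0 − 42.1 = −2.1

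Each arm therefore moves by about 2 to 3 points, in either direction.

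**Step 4: against the reported uncertainty.** The SAP uses Clopper-Pearson limits. For 8/19 these are the 2.5% point of Beta(8, 12) and the 97.5% point of Beta(9, 11), that is 20.3% to 66.5%. A 2- to 3-point shift lies well inside that interval.

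**Step 5: a sham/ocriplasmin mismatch.** Assume rates of 40% and 5% (9.1) and that response follows the treatment received. The expected as-received difference is 40 − 5 = 35.0 points. The as-randomised difference with one mismatch is:
- one of 19 ocriplasmin subjects given sham first: (18 × 0.40 + 1 × 0.05)/19 − 0.05 = 33.2 points, a gap of 1.8
- one of 10 sham subjects given ocriplasmin first: 0.40 − (9 × 0.05 + 1 × 0.40)/10 = 31.5 points, a gap of 3.5

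**Step 6: no mismatch.** If every first injection matched its assignment, the two groupings contain the same subjects in the same arms and every table is identical. The documents do not state the number of mismatches.

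**The case against.** The case for leaving the rule alone has real substance.

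- **No inference depends on it.** Recruitment stopped at 48 of 115 and the SAP drops all testing, so no p-value or hierarchical step rests on the grouping. This stands and limits the severity.
- **No mismatch is reported, and controls exist.** The treatment number comes from IXRS and loads automatically into the eCRF (3.5.1). An unmasked monitor checks that assigned treatments were correctly given (6.2.5). Deviations are reviewed before database lock (SAP section 3). This stands: the documents give no evidence that any subject changed arm.
- **A wrong saline volume moves nobody by itself.** It matters only if it is detected and recorded as a different treatment received, and the documents do not say that the added volume is captured. A sham/ocriplasmin mix-up is less likely still, because the vials look different and the person injecting is unmasked. Both stand.
- **The rule is not concealed.** It is printed in the opening paragraph of SAP section 3. What is missing is its identification as a change from the protocol.
- **As-received results can be informative.** In Step 5 the as-received difference keeps the full 35.0 points and the as-randomised one is diluted. That depends on the assumption that response follows the treatment received. It does not make the result the one the protocol specified.
- **The public SAP is abbreviated.** Mock-up tables and listings were removed, so a listing of assigned against received treatment may exist. That would help with transparency but would not alter the printed grouping rule.

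A reader might infer from the responder row in Step 3 that the rule creates a spurious 6-point dose effect. The documents do not support that: the figure assumes a mismatch that is not reported and a responder as the subject who moves. A non-responder gives 4.4 points in the opposite direction.

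**Conclusion.** The two documents disagree. The protocol groups efficacy as randomised, the SAP groups it by first injection received, and neither list of changes identifies the switch. The SAP's abbreviation does not explain this, because the rule is complete as printed.

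The size is modest and conditional. It is zero if no recorded first injection differed from the assignment. Otherwise, one subject moved between dose arms shifts each arm's proportion by about 2 to 3 points in either direction, assuming arms of about 19/19/10 and a response rate near 40%. Only descriptive proportions, means and confidence intervals are affected.

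Two stronger readings are tempting and unsupported. One is that the efficacy comparison has already lost the protection of randomisation, which would require mismatches that the documents do not report. The other is that subjects given sham at Day 35 or Day 70 after achieving total PVD change arm. They do not, because only the first injection counts.

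Severity: moderate to minor. It is worth correcting because the correction is cheap and restores the protocol's own rule for the primary endpoint.

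**What to change.** 1. Keep the single set of randomised and treated subjects, and replace the arm rule in SAP section 3 with, for example: *Efficacy and baseline tables present subjects by randomised arm; safety tables present subjects by the first injection received.* Protocol 9.4 does not name an arm rule for baseline tables. Randomised arm is proposed there so that they match the efficacy tables.
2. Add a listing of every subject whose randomised arm and first injection received differ. If there are none, say so and state that the two groupings coincide.
3. If any efficacy table stays grouped by treatment received, add that to the SAP's list of changes from the protocol and to the clarification note.

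The SAP's Background describes the final analysis as having taken place. If the SAP can no longer be revised, the same statement and listing can go in the clinical study report, where protocol 9.3 already places deviations from the SAP.

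Cost: one or two sentences and one listing, with no new data. IXRS assignments and the unmasked accountability records supply the comparison. Efficacy tables need re-running only if a mismatch is found.
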